3 OBJECTIVES AND ENDPOINTS

3.1 Primary Objectives and Endpoints

Primary Objective

- Evaluate the safety and tolerability of the injectable agent, GSK1265744 long acting (744LA) injectable (800 mg dose administered at three time points at 12 week intervals) through Week 41 in HIV-uninfected men and women
- Evaluate the safety and tolerability of the injectable agent GSK1265744 long acting (744LA) injectable (600 mg dose administered at two time points at 4 week intervals, followed by three time points at 8 week intervals), through Week 41 in HIV-uninfected men and women.

Primary Endpoints

Safety endpoint: Proportion of participants experiencing any Grade 2 or higher clinical AEs and laboratory abnormalities that occur from the initial injection to 12 weeks after the last injection among participants who receive at least one injection (injectable phase only)

Tolerability endpoint: Proportion of participants who receive at least 1 injection and who discontinue receiving injections prior to the full course of 3 injections due to intolerance of injection (including but not limited to ISR), frequency of injections, burden of study procedures, or any AE.

These cohorts may be aggregated for an overall analysis if appropriate.

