9.5.2 AEs

AEs will be summarized using MedDRA system organ class and preferred terms. The number and percentage of participants experiencing each specific AE within a System Organ Class or within preferred term will be tabulated by severity or by relationship to study product within each treatment arm. For the calculations in these tables, a participant with multiple AEs within a category during the evaluating phase of the study will be counted once under the maximum severity or the strongest recorded causal relationship to study product. AEs will be summarized for those that will occur during the injection phase separately from those that will occur during the oral phase and as well as for those that will occur during the entire treatment phase of the study (the oral and the

injection phase). AEs leading to temporarily or permanently stopping drug will also be summarized by treatment arm.

A listing of EAEs reported to the DAIDS RSC Safety Office will provide details of the events including severity, relationship to study product, time between onset and last injection, number of injections received, and a summary of the event.

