9.5.5 Safety Endpoint

Primary safety endpoint is the proportion of participants experiencing any Grade 2 or higher clinical AEs or laboratory abnormalities since the initial injection to 12 weeks (8 weeks) after the last injection in Cohort 1 (Cohort 2) among the participants who complete at least one injection to evaluate the safety of the 744 injectable during the injection phase. A secondary safety endpoint is the proportion of Grade 2 or higher clinical AEs or laboratory abnormalities occurred from the initial injection to 76 weeks in both cohorts after last injection among the participants who complete at least one injection to evaluate the safety of the 744 injectable in long term; the proportion of Grade 2 or higher AEs or laboratory abnormalities occurred during the oral phase (Weeks 0-5) among all enrolled participants to evaluate the safety of the oral 744 product; and the proportion of Grade 2 or higher AEs or laboratory abnormalities occurred during the whole study period among the all enrolled participants to evaluate the safety of the oral and injectable product. The proportions of endpoints and the %95 confidence intervals will be estimated for each treatment arm. The 95% CIs will be estimated using Wilson score method¹. The proportions of endpoints will be compared between the treatment arms using Fisher Exact test.

In addition, the safety endpoint rate might be calculated for each treatment arm and compared between the treatment arms. The safety endpoint rate is the number of the participants who have experienced Grade 2 or higher clinical AEs or laboratory abnormalities during the study period (defined in each safety analysis) divided by the person-time-at-risk throughout the observation period within the study period.

The 95% exact confidence interval of the safety event rate will be calculated for each treatment arm, assuming the rate follows the Poisson distribution. The safety event rate will be compared between the treatment arms using exact Poisson test.

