Appendix

Definition of Derived Variables and Study Populations

Study Populations:

Randomized population: randomized=1 if Screnr = 1 (Form SO-1 006, screening outcome)

Oral safety analysis population: randomized=1 and PCpdn>0 and PCpbrp="No", or PCpdn>Pcnumpil if PCpbrp="Yes" (Form PC-1 134, Pill count)

Primary/Injectable safety analysis population: randomized=1 and Iaingiv=1 for week5 (Form IA-1 126, Injection administration)

Derived Variables:

BMI=weight (in kg)/ height(in cm)*height(in cm) (Form LLR-1152, Local Laboratory Results)

Algorithm of defining the phase for AEs

The phase (oral or injection) of AEs was determined based on the AE on-set date and the first injection date as follows.

For AEs with a complete onset date (no missing on day, month, or year)

1. If the AE onset date is before of the first injection date, then the phase of the AE is oral.
2. If the AE onset date is after the first injection date, then phase of the AE is injection.
3. If the AE onset date is on the same date as the first injection date, then:
 - a. If the AE is Injection site reaction, then the phase of the AE is injection.
 - b. If the AE is not Injection site reaction, then the phase is oral.

For the AEs with an incomplete onset date (missing day, day is not mandated)

1. If the onset date is before the first injection date determined by the month and the year of the onset date, then the phase is oral.
2. If the onset date of the AE is after of the first injection date determined by the month and the year of the onset date, then the phase is injection.
3. If the month and year in the AE onset date match to the month and year in the first injection date, then:
 - a. the sites determined whether the AE occurred before or after the first injection.
 - b. If the sites could not determine, PI determined which phase the AE should be.

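### AE phase is set by onset date only, with no rule for an AE that starts before the first injection and worsens to Grade 2 or higher after it

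*SAP*

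**What the plan says.** The phase algorithm is in the SAP Appendix, and its stated basis is two dates: "The phase (oral or injection) of AEs was determined based on the AE on-set date and the first injection date as follows". For complete dates, the first rule is "If the AE onset date is before of the first injection date, then the phase of the AE is oral". Later onset gives injection phase. Same-day onset is split between injection site reactions and everything else. When the day is missing and the month matches, the site decides, and failing that the PI. Grade plays no part in any branch.

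The primary safety endpoint depends on grade and time together. Section 3.1 counts participants with "any Grade 2 or higher clinical AEs and laboratory abnormalities that occur from the initial injection", and Section 9.5.5 starts the window at the same point: "Primary safety endpoint is the proportion of participants experiencing any Grade 2 or higher clinical AEs or laboratory abnormalities since the initial injection".

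Section 9.5.2 has a maximum-severity rule for the AE tables: "a participant with multiple AEs within a category during the evaluating phase of the study will be counted once under the maximum severity". Section 9.5.3 brings laboratory abnormalities that lack a clinical diagnosis into the AE tabulation. Section 8 leaves the details of data collection to Section 12 of the SSP manual, which is not shown.

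**The concern.** The date that decides the phase is the date an event began at any grade. The date that matters for the endpoint is when the event reached Grade 2 or higher. The two differ for an event that is mild at the end of the oral lead-in and becomes worse after the injection. The Appendix handles same-day onsets and missing days in detail, but not this case.

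Within an arm the error can go only one way: rule 1 can take such an event out of the injection phase but cannot add one. What would be at stake is the primary safety proportion in each arm. The long-term secondary endpoint in Section 9.5.5 is also exposed, because its window opens at the first injection too. The effect on the comparison between arms has no known direction, since the rule is the same in both arms and the SAP gives no worsening rates.

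**Working it through.** The SAP states no figure on this point, so there is nothing to reproduce. The check has two parts.

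**1. One event under two recording conventions.** Take a hypothetical headache, Grade 1 with onset at Week 4 and Grade 2 at Week 9, with the first injection at Week 5 (Section 2.3).

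- *A grade increase opens a new AE record.* The new record has onset at Week 9, after the first injection. The second Appendix rule gives injection phase. The event is in the primary endpoint and nothing is lost.
- *The grade is updated on the existing record.* Onset stays at Week 4 and rule 1 gives oral phase. The Grade 2 episode is outside the primary endpoint, although Section 7.1 ends the oral phase on the day of the first injection.

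The SAP does not say which convention applies. In the second case it also does not say which grade the record carries into the oral-phase tables.

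**2. What one participant is worth.** Arm sizes are from Section 2.4; those for Cohort 2 are approximate.

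- Cohort 1 active: 1/82 = 1.2 points
- Cohort 2 active: 1/66 = 1.5 points
- Cohort 1 placebo: 1/28 = 3.6 points
- Cohort 2 placebo: 1/22 = 4.5 points

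These are randomized numbers. The endpoint denominator is those who were injected, so one participant weighs at least this much if some never reach injection.

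**Illustration under assumed rates.** Let f be the share of participants with an oral-onset AE that first reaches Grade 2 or higher after injection. Let q be the chance that such a participant also has another Grade 2 or higher event in the injection phase. The endpoint counts participants, so under the second convention:

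expected loss = f × (1 − q)

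- Low end, f = 1%, q = 90%: 0.01 × 0.10 = 0.1 points, or 82 × 0.001 = 0.1 participants in Cohort 1 active
- Middle, f = 3%, q = 60%: 0.03 × 0.40 = 1.2 points, or 1.0 participant
- High end, f = 5%, q = 30%: 0.05 × 0.70 = 3.5 points, or 2.9 participants

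On precision, suppose 49 of 82 (59.8%) reach the endpoint. The Wilson 95% interval is 48.9 to 69.7. Losing two participants gives 47 of 82 (57.3%), interval 46.5 to 67.5. The shift is small against the width of the interval. All values of f, q and the event count are assumptions. Under the first convention the loss is zero.

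**The case against.** The strongest objection is that the misclassification depends on a recording convention the SAP leaves to a manual that is not shown. If worsening opens a new record, the Appendix already gives the right phase. This stands, and the point is conditional because of it. It does not remove the point: the Appendix sets its own phase rule and neither relies on nor cites such a convention.

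A reader might infer from Section 9.5.2 that every AE carries the highest grade it ever reached, so that a post-injection Grade 3 would certainly be shown as oral toxicity. The text does not support that. Its maximum is taken over several AEs of one participant, within a category and within the phase under evaluation. It says nothing about the lifetime maximum of a single AE.

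Laboratory worsening is also less exposed than clinical worsening. Section 9.5.3 tabulates graded laboratory values by visit, and Section 9.5.4.2 summarises the maximum liver toxicity separately for each phase. A rise after injection would be visible there. The SAP does not say that these summaries feed the primary endpoint, so the exposure is reduced but not excluded.

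Finally, no event disappears from the trial. Section 9.5.2 also summarises the oral and injection phases together, and Section 9.5.5 has a whole-study Grade 2 or higher endpoint. That is correct, but neither is the primary endpoint.

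**Conclusion.** The point holds in conditional form. Phase follows onset date, the primary endpoint depends on reaching Grade 2 or higher after the first injection, and no rule connects the two for an AE that straddles that injection. A participant is lost from the primary endpoint only if both of these hold:

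1. the grade increase is made on the existing record, which keeps its onset date; and
2. the participant has no other Grade 2 or higher clinical event or laboratory abnormality in the injection phase.

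The size is unknown. The range of 0.1 to 3.5 points rests wholly on assumed rates, and zero is possible. It would go too far to say that events are missing from the endpoint as a matter of fact, or to state how many participants are affected, because the SAP gives neither the recording rule nor any rates. This is a cheap improvement that protects the primary endpoint under either convention, not a demonstrated error in the result.

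**What to change.** Add one rule to the Appendix algorithm: an AE with onset before the first injection also counts as an injection-phase event, dated at the grade increase, if its grade after the first injection is 2 or higher and exceeds its grade just before that injection. Under this rule:

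- Grade 1 rising to Grade 2 or 3 counts in the injection phase.
- Grade 2 rising to Grade 3 counts in both phases, at its own grade in each.
- Grade 2 that merely persists at Grade 2 does not count again.

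For laboratory abnormalities, take phase and grade directly from the dated graded values. In the AE tables, state that severity is the maximum grade within each phase.

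If the SSP manual already opens a new AE record at every grade increase, cite that rule in the Appendix; the added rule then changes nothing.

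The cost is a few lines of SAP text and minor programming, plus a few site queries for clinical AEs that straddle the first injection without a recorded date of grade change.

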7 ASSESSMENT WINDOWS

7.1 Treatment Periods

Adverse events, laboratory, vital signs and liver events will be assessed and denoted within the treatment periods that are defined below.

Oral Phase is defined as the time between the enrollment date (Week 0) and the day of the 1st injection (Week 5) or the day of withdrawal, whichever comes first.

Injection Phase is defined as the time between the first injection and the 12 weeks visit after the last injection. For the participants who complete all three injections, the injection phase assessment window is the time between Week 5 and Week 41 visits. For the participants who complete the two injections, the injection phase assessment window is the time between Week 5 visit and Week 29 visit. For the participants who complete only the first injection, the injection phase assessment window is the time between Week 5 visit and Week 17 visit.

Tail Phase is defined as the time between Week 41 to Week 105/109 for ITT analysis. However, for per protocol analysis such as pharmacokinetics analysis, for the participants who did not complete full injections (3 injections for cohort 1 and 5 injections for cohort 2), the tail phase assessment window starts at the 12th (the 8th) weeks after the last injection for cohort 1 (cohort 2) to the last follow-up visit.

On-Treatment is defined as the time between the beginning of the oral phase and the end of the follow-up phase (from the participants' enrollment day to the participants' last day subject's last day in the study).

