7.2 Baseline Definition

The data collected at the enrolment date will be considered as the baseline data for monitoring and evaluating the safety, tolerability, and acceptability of the investigating study product and other analyses unless it is specified. In some cases, the assessments at Week 5 prior to the first injection will be considered as the baseline.

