9.5.3 Local Laboratory Values

Scatter plots of some local laboratory values measured during the course of the study vs. the values at the baseline. If appropriate, horizontal/vertical lines representing boundaries for abnormal values will be plotted.

For each local laboratory measure, summary statistics will also be presented by treatment arm and visit time, as well as changes from baseline for post-enrollment values. Clinical laboratory abnormalities without an associated clinical diagnosis will also be reported as AEs and will be included in the tabulation of AEs described above.

In addition, the number (percentage) of participants with local laboratory values recorded as meeting Grade 1 AE criteria or above as specified in the DAIDS AE Grading Table (see Section 6.4.2 of the protocol) will be tabulated by treatment arm for each safety visit time point. In addition to SAEs, a list of the participants with the results: ALT \geq 3xULN and bilirubin \geq 2xULN will be provided.

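### SAP Appendix rule 3b counts non-ISR adverse events that begin after the first injection on the same day as oral-phase events, although the primary safety window opens at that injection

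*SAP*

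**What the plan says.** Section 3.1 defines the primary safety endpoint by Grade 2 or higher clinical events and laboratory abnormalities "that occur from the initial injection to 12 weeks after the last injection", among participants with at least one injection. Section 9.5.5 repeats the same start: "since the initial injection to 12 weeks (8 weeks) after the last injection in Cohort 1 (Cohort 2". (The two sections differ on when the window ends for Cohort 2, which does not bear on this point.) Section 7.1 agrees on the start: "Injection Phase is defined as the time between the first injection and the 12 weeks visit after the last injection".

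Section 7.1 also says: "Oral Phase is defined as the time between the enrollment date (Week 0) and the day of the 1st injection (Week 5". It does not state whether that day belongs to the oral phase.

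The Appendix gives the algorithm that assigns a phase to each adverse event. For complete dates, onset before the first-injection date is oral and onset after it is injection. On the date itself, rule 3a sends injection site reactions (ISRs) to the injection phase. Rule 3b covers the rest: "If the AE is not Injection site reaction, then the phase is oral". For an event whose onset day is missing and whose month and year match those of the injection, the Appendix instead has the site decide whether it came before or after the injection, and the PI decide if the site cannot.

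Table 19 (section 11.2.1) reports the Grade 2 or higher proportion separately for the oral and injection phases, so the algorithm feeds the primary result.

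**The concern.** The endpoint definition uses a moment, the injection. Rule 3b uses a calendar date and resolves the tie one way for all non-local events. A Grade 2 or higher non-ISR event that starts an hour after the first injection meets the definition of the primary endpoint but is not counted in it. It is counted in the secondary endpoint meant to describe the oral product: "laboratory abnormalities occurred during the oral phase (Weeks 0-5) among all enrolled participants".

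The day concerned is the first exposure to a long-acting injectable. Systemic reactions on that day are ones the primary safety endpoint, as defined, should count. Relative to the stated definition, the rule can only lower each arm's injection-phase proportion or leave it unchanged, and can only raise the oral-phase proportion or leave it unchanged.

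**Working it through.** **Step 1. Compare the rule with the definition.** Every possible case for a fully dated event, with the phase from the Appendix set against the window that opens at the injection:

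| Onset date | Type | True timing | Appendix | Definition |
|---|---|---|---|---|
| Day before or earlier | non-ISR | before | oral | oral |
| Day before or earlier | ISR | before | oral | oral |
| Same day | non-ISR | before | oral | oral |
| Same day | non-ISR | after | **oral** | **injection** |
| Same day | ISR | before | injection | oral |
| Same day | ISR | after | injection | injection |
| Day after or later | non-ISR | after | injection | injection |
| Day after or later | ISR | after | injection | injection |

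Six of the eight cases agree. An ISR before any injection cannot occur in practice. That leaves one real mismatch: the same-day, post-injection, non-ISR event. Nothing elsewhere in the SAP overrides rule 3b.

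**Step 2. Share of the window.** Weeks 5 to 41 give (41 − 5) × 7 = 252 days, and 1/252 = 0.4%. This measures time. It does not bound the effect, because acute reactions could cluster on that day.

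**Step 3. Shift per affected participant.** A participant changes status only if the same-day event is their sole Grade 2 or higher event in the window. The shift is then 1/n. The arm sizes are from section 2.4; those for Cohort 2 are given there as approximate. All randomised participants are assumed to have been injected. If fewer were, each shift is larger.

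| Arm | n | Shift (percentage points) |
|---|---|---|
| Cohort 1 active | 82 | 100/82 = 1.2 |
| Cohort 1 placebo | 28 | 100/28 = 3.6 |
| Cohort 2 active | 66 | 100/66 = 1.5 |
| Cohort 2 placebo | 22 | 100/22 = 4.5 |
| Both cohorts, active | 82 + 66 = 148 | 100/148 = 0.7 |
| Both cohorts, placebo | 28 + 22 = 50 | 100/50 = 2.0 |

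**Step 4. Scale against the planned interval.** Section 9.5.5 uses the 95% Wilson interval, whose half-width is

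z/(1 + z²/n) × √[p(1 − p)/n + z²/(4n²)], with z = 1.96.

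The SAP gives no expected proportion, so a range of counts is assumed:

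| n | Assumed counts | Half-widths (points) |
|---|---|---|
| 82 | 25, 41, 57, 74 | 9.8, 10.6, 9.8, 6.5 |
| 28 | 8, 14, 20, 25 | 15.9, 17.4, 15.9, 11.7 |

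Example: 41/82 = 50.0% (39.4 to 60.6) becomes 40/82 = 48.8% (38.3 to 59.4). One moved participant stays well inside the interval.

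**The case against.** The best defence is that rule 3b has some support in the SAP. If the oral phase in section 7.1 includes the day of the first injection, rule 3b carries that sentence out, and rule 3a carves out the one event type that must follow the injection. The algorithm works on dates, and the SAP shows no onset clock time, so some default is needed and either default misplaces some events. Sending all same-day events to the injection phase would bring in findings made before dosing. Section 7.2 provides that in some cases "the assessments at Week 5 prior to the first injection will be considered as the baseline", and section 9.5.3 adds: "Clinical laboratory abnormalities without an associated clinical diagnosis will also be reported as AEs". A fixed rule also keeps judgement out of a primary endpoint, and using site judgement for a missing day, where the uncertainty can span most of a month, does not oblige the plan to use it within one day. The rule is the same in both arms, and no event is lost from the oral-plus-injection or on-treatment summaries.

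Much of this stands. Rule 3b suits Week 5 findings made before the injection, and a tie-break is needed. But an inclusive reading of the oral phase only makes the two phases overlap on that day. It does not reconcile the rule with sections 3.1 and 9.5.5. Date-only data justify a default for events whose order is unknown, not one applied to clinical events known to have followed the injection. The Appendix's own before-or-after determination needs no clock time.

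**Conclusion.** The point holds. As written, the derivation of a primary endpoint does not match its definition for one identifiable class of events: same-day, post-injection, non-ISR events with a complete date.

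The numerical effect is probably small: 0.7 to 4.5 percentage points per affected participant, depending on arm and cohort, under the assumption that everyone randomised was injected. The SAP does not allow the number affected to be estimated. Both arms receive injections, so the direction of any effect on the arm comparison is open. The reason to act is the mismatch itself and the low cost of removing it. A changed conclusion is not likely.

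**What to change.** Replace rule 3b so that a non-ISR event dated on the first-injection day is classified by whether it began before or after the injection, using the site-then-PI determination the Appendix already applies to incomplete dates, made blinded to arm. Keep abnormalities from pre-injection Week 5 samples or assessments in the oral phase. Count events whose order cannot be determined in the injection phase, with a sensitivity analysis that assigns them to the oral phase. State the same boundary convention in section 7.1, so that the two phases no longer share a day.

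The Appendix is written in the past tense, so phases may already have been assigned. If so, or if a blinded determination is no longer possible, keep rule 3b and report a sensitivity analysis of the primary endpoint that moves same-day non-ISR clinical events to the injection phase.

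The main option costs SAP wording, a small derivation change and a few site queries, limited to one calendar day per participant and completed before the unblinding described in section 4.8. The fallback costs one extra table. The downside of the main option is that a few pre-injection events of unknown order may count against the injectable; its sensitivity analysis would show how many.
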